Protocol Abstract Page

A Phase 1/2 Open-Label Study of TPI 287 in Patients with Breast Cancer Metastatic to the Brain 2010-0198

Core Protocol Information

Study Chairman:	[name]
Department:	Breast Medical Oncology
[contact]
Unit:	1354
Full Title:	A Phase 1/2 Open-Label Study of TPI 287 in Patients with Breast Cancer Metastatic to the Brain
Protocol Phase:	Phase II
Version Status:	Terminated 04/18/2017
Version:	11
Document Status:	Final

Abstract

Objectives:

Primary objective (Phase 1)

To evaluate the maximum tolerated dose (MTD) and safety of TPI 287 administered once every three weeks in patients with refractory or recurrent breast cancer metastatic to the brain

Primary objective (Phase 2):

To estimate the efficacy of TPI 287 by assessing the overall response rate [ORR (CR + PR)] of recurrent brain metastases using the McDonald Criteria.

Secondary objectives (Phase 1 and 2):

- a. To evaluate response duration of breast brain metastases on TPI 287
- b. To evaluate rate and duration of the clinical benefit (CR+PR+SD)
- c. To assess activity of TPI 287 on extracranial metastatic disease
- d. To measure median progression free and overall survival of patients with metastatic breast cancer treated with TPI 287

Rationale: (Be as concise as possible)

The current study proposes to examine a novel microtubule inhibitor TPI 287 that has shown potency and efficacy in a number of taxane sensitive and resistant tumors in

both preclinical and clinical studies. TPI 287 has also been shown to be very well tolerated and exhibits limited myelosuppression at the currently employed doses. It has also been shown that IV TPI 287 can penetrate the brain parenchyma to reach pharmacologically and clinically relevant levels, which suggests that breast cancers metastatic to the brain would be an appropriate target for therapy. There is a significant amount of human safety data for TPI 287 with over 100 adult patients and now 5 pediatric patients who have received drug in prior clinical trials to adequately assess the safety of the clinical trial and the dosing regimen for TPI 287 planned.

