During Phase 1, the dose of TPI 287 will be escalated in sequential dose cohorts (inter-cohort dose escalation). TPI 287 will be administered at an initial dose of 160 mg/m² as a 60-minute (\pm 10 minutes) intravenous (IV) infusion once every three weeks (i.e., 1 cycle = 21 days). If patients enrolled at this dose have no dose limiting toxicities (DLTs) within 21 days of receiving the first dose of study drug, additional patients will be enrolled in subsequent cohorts of 3 patients at 20 mg/m² increments (180 mg/m², 200 mg/m², 220 mg/m², etc.) to explore a maximum tolerated dose (MTD) on this schedule for this patient population. If patients experience DLT at the starting dose, one dose level below (Level -1) is also proposed.

If 1 out of 3 patients experiences a DLT within 21 days of receiving the first dose of study drug, an additional 3 patients will be enrolled in that cohort. If \geq 2 patients at

any dose level experience DLT within 21 days of receiving the first dose of study drug, the MTD will be the previous dose level tested.

The MTD determination will be based on the number of patients that experience DLTs within 21 days of receiving the first dose of study drug. DLTs will be considered to be any hematologic toxicity \geq Grade 3 within 21 days of receiving the first dose of study drug that does not recover within 3 weeks or any non-hematological toxicity \geq Grade 3 within 21 days of receiving the first dose of study drug that does not improve to Grade 1 or baseline within 3 weeks

Patients on the Phase 2 portion of the study will be enrolled at the MTD determined during Phase 1. Initially, 25 patients will be enrolled in the Phase 2 portion of the trial; if at least 5 patients are shown to have an objective response, an additional 26 patients will be enrolled.

Patients may continue treatment in the study at any dose until intracranial disease progression or death, unacceptable toxicity, withdrawal of consent, or discontinuation based on Investigator discretion. Patients will be followed for survival for up to 1 year after enrollment on the study.

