Intra-patient dose escalation will be allowed for patients with extracranial progressive disease as long as the response of intracranial disease is stable or better and there is no unacceptable toxicity. Only one dose escalation will be allowed per patient. The dose will be escalated to the next higher dose level (20 mg/m² increase); under the condition that this higher dose level was previously shown to be safe per the inter-cohort dose escalation criteria.

Table of Procedures and Assessments:

Event	Screen	Cycle 1			Cycle 2	Subsequent Cycles	Follow-Up Visit 28 ±2 days after last dose
		Day 1	Day 8	Day 15	Day 1		
Informed consent	X ²						
Medical & surgical history ^a	X ⁴						
Prior history and therapy for breast cancer ^b	X ⁴						
Demographics	X ⁴						
Physical examination ^c	X ⁴					X ³	X
Vital signs ^d	X ⁴	X				X ^{3, 6}	X
ECOG performance status	X ⁴	X ¹				X ¹	X
Laboratory Studies ^e	X ³	X ¹	X	X	X	X ¹	X
Urinalysis ^e	X ³						
Pregnancy test ^f	X ³						
Brain Gd-MRI ^g	X ²					X ⁷	X ³
Extracranial disease assessment ^g	X ²					X ⁷	X ³
Concomitant medications ^h	X ⁴	X ⁴				X	X
BSA calculation ⁱ		X ⁴				X ¹	
Administration of TPI 287 ^j		X ³			X ³	X ³	
AE monitoring ^k	X	X				X ¹	X
Survival ^l						X	X

Description/Definitions of Procedures and Assessments	Timing
a Complete medical and surgical history to include pertinent medical conditions and a careful history of all prior medical treatments	1 Prior to dosing with study drug within 7 days of each cycle unless otherwise specified
b Complete history of breast cancer to include date of diagnosis, histologic evidence of disease, dates of prior therapies (including surgery, radiation, chemotherapy) as well as date of documented recurrence/progression	2 Within 28 days of first dose of study drug
c Physical examination (including height and weight), noting all baseline abnormalities including neurologic exam	3 Within 14 (\pm 3 days) of first dose of study drug
d Temperature, pulse rate, blood pressure (sitting)	4 Within 7 days (\pm 3 days) days of dose of study drug

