e Complete blood count, including RBC, MCV, MCH, MCHC, hemoglobin, hematocrit, WBC with differential, and platelet count (WBC with differential and platelets will be collected weekly for 1 st cycle and within 7 days of each subsequent cycles); additional labs to be obtained at these time include sodium, potassium, chloride, bicarbonate, calcium, glucose, BUN, creatinine, albumin, total protein, alkaline phosphatase, total bilirubin, ALT, AST; Dipstick determinations of urinary protein, glucose, ketones, hemoglobin, and bilirubin, but only for the first three cycles and/or if clinical indicated. Patients who are taking coumadin (warfarin) will have PT, PTT, and INR prior to each cycle of treatment. Patients who have 2+ or greater hemoglobin or protein on a spot urine must have a microscopic examination performed. Urine exam is done only at screening.	5 Prior to dosing as interim update (only note changes from prior record). To be obtained within \pm 3 days.
f For females of childbearing potential only, may be based on serum or urine testing	6 Prior to dosing with study drug and immediately following 60 minute infusion
g Brain Gd-MRI must be obtained as per protocol. Extracranial disease assessments may include CT/MRI scans of chest, abdomen, pelvis as well as bone scans, and as per standard of care otherwise indicated by treating physician. All disease assessments will be performed when clinically indicated.	7 Within 7 days prior to odd numbered cycles
h All medications/therapies used within 30 days prior to first dose of study drug	8 If scan has not been obtained within previous 2 cycles
i If weight fluctuates \pm 10% from prior measurement, new BSA will be used to calculate next dose	9 Within (\pm 1 day)
j One hour IV infusion of TPI 287 Injection on day 1 every 21 days. See Section 5 for Study Drug Administration.	
k All drug-related toxicities must be followed for resolution. Patients are to be followed for up to 30 days (\pm 5 days) after last drug administration for adverse events, regardless of causal relationship.	
l Data will be collected every 3 months from the time the patient is off-treatment up to a period of 1 year from the patient's date of enrollment	

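### Patients who stop TPI 287 without progression have no planned capture of a later progression date, so median PFS and duration of clinical benefit risk being overstated (minor; secondary endpoints only)

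*Combined protocol and SAP*

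**What the plan says.** The Objectives section lists, for both phases, "To measure median progression free and overall survival of patients with metastatic breast cancer treated with TPI 287" and "To evaluate response duration of breast brain metastases on TPI 287". A further objective covers how often clinical benefit (CR, PR or SD) occurs and how long it lasts.

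Under Proposed Treatment/Study Plan, treatment can end before progression through "unacceptable toxicity, withdrawal of consent, or discontinuation based on Investigator discretion". The same section then provides for survival follow-up to one year from enrollment and mentions no other follow-up.

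In the Table of Procedures and Assessments, the on-treatment timing that applies to brain MRI and extracranial assessment is "Within 7 days prior to odd numbered cycles". The last column is "Follow-Up Visit 28 ±2 days after last dose", and both imaging rows are marked in it. There is no later column. Footnote l, on the Survival row, reads "Data will be collected every 3 months from the time the patient is off-treatment", to a limit of one year from enrollment. Footnote g adds that disease assessments are done when clinically indicated.

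Statistical Considerations defines the analysis populations and the two-stage response-rate design. It gives no definition, event rule or censoring rule for PFS or for any duration.

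**The concern.** PFS and duration of clinical benefit both need a progression date. The imaging schedule is tied to treatment and ends with the 28-day visit, whereas the reasons for stopping include two, toxicity and investigator discretion, that can apply to a patient who has not progressed. For such a patient, the plan as written leaves two likely routes in the analysis.

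- **Censor at the last assessment.** This is unbiased only if patients who stop have the same later progression risk as those who continue. If stopping tends to come shortly before progression, the estimated median is too long.
- **Count death as the next event.** Deaths are collected to one year. A progression that was not recorded is then dated at death, which lengthens PFS even when stopping is unrelated to progression.

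Both errors run in the favorable direction, and a single-arm trial has no control group that shares them.

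**Working it through.** **The plan's own figure.** The only calculated figures concern response rate: 25 + 26 patients, continue with at least 5 responders, success with at least 11 of 51. Exact two-stage binomial sums give alpha 0.1068 (stated 11%), beta 1 − 0.8763 = 0.1237 (stated 12%) and early termination under 15% of 0.6821 (stated 68%). All reproduce, and none depends on follow-up after treatment.

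**Inputs for the illustration.** None of these is in the documents: exponential progression on treatment with median 3 months; a share f = 20%, 30% or 40% stopping before progression; a progression hazard h times higher after stopping, h = 1, 2 or 4. A month is 30.44 days.

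- Progression hazard on treatment: λ = ln 2 / 3 = 0.2310 per month.
- Stopping hazard: σ = λf/(1 − f) = 0.0578, 0.0990, 0.1540.
- Let a = λ + σ − hλ. True PFS curve: S(t) = exp(−(λ+σ)t) + σ exp(−hλt)[1 − exp(−at)]/a.
- Suppose progression is observed for d months after stopping and the patient is then censored. Among patients under observation, the ratio of stopped to on-treatment patients is q(t) = σ[exp(a·min(t,d)) − 1]/a. The observed hazard is λ(1 + hq)/(1 + q), and the Kaplan-Meier median is where its integral reaches ln 2.

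**How much the 28-day scan buys.** The 28 days run from the last dose. If stopping is decided when the next 21-day dose is due, 28 − 21 = 7 days remain. So d is taken as 0, 7 or 28 days.

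**One case in full** (f = 40%, h = 4, d = 28 days = 0.92 month). a = 0.2310 + 0.1540 − 0.9242 = −0.5391. At d, q = 0.1540 × (1 − e^−0.496)/0.5391 = 0.112, and the hazard is 0.2310 × 1.447/1.112 = 0.301. The integral is 0.248 at d; the remaining 0.445/0.301 = 1.48 months gives a median of 2.40. The true median is 2.28, so the excess is 5%.

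| f | h | True median (months) | d = 0 | d = 7 days | d = 28 days |
|---|---|---|---|---|---|
| 20% | 2 | 2.82 | 3.00 (+6%) | 2.96 (+5%) | 2.89 (+2%) |
| 20% | 4 | 2.65 | 3.00 (+13%) | 2.90 (+9%) | 2.73 (+3%) |
| 30% | 2 | 2.72 | 3.00 (+10%) | 2.94 (+8%) | 2.81 (+3%) |
| 30% | 4 | 2.47 | 3.00 (+22%) | 2.83 (+15%) | 2.57 (+4%) |
| 40% | 2 | 2.61 | 3.00 (+15%) | 2.90 (+11%) | 2.72 (+5%) |
| 40% | 4 | 2.28 | 3.00 (+32%) | 2.75 (+21%) | 2.40 (+5%) |

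With h = 1 the observed hazard is λ throughout, so censoring gives no bias.

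**Dating missed progressions at death.** Take h = 1, credit the full 28 days, and assume a median of 4 months from progression to death (μ = ln 2 / 4). Progressions missed at time x have density λ exp(−λx)[1 − exp(−σ(x − d))] for x > d. The reported curve is exp(−λt) plus the integral of that density times exp(−μ(t − x)) from d to t. Its medians are 3.14, 3.25 and 3.43 months for f = 20%, 30% and 40%, against a true 3.00: about 5%, 8% and 14% too long.

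**Against sampling error.** With a 3-month exponential median, the 95% range of a sample median is about 2.0-4.3 months at 51 patients and 1.6-5.0 at 25.

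**The case against.** The strongest reply is that the plan does not commit to a biased analysis. No censoring rule is stated, so a reader who infers that these endpoints are informatively censored goes further than the text. That holds only if stopping predicts progression, which is plausible for toxicity or discretion but which the documents do not show. This part of the reply stands: the supported wording is that the endpoints are at risk.

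Nor do the documents support the inference that a later progression is never captured. Footnote g foresees clinically indicated scans, all patients are at one center, and footnote l does not list its fields. But footnote g sets no schedule after treatment and does not say that such results enter the trial record, and footnote l sits on the Survival row. The gap in planned capture remains. Footnote j refers to a Section 5 outside these documents, so missing definitions may exist elsewhere.

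A reader might also count response duration as a third affected endpoint. Its objective, "To evaluate response duration of breast brain metastases on TPI 287", can be read as an on-treatment quantity that needs no later scans. The documents do not settle this, so it is affected only on the other reading.

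Finally, the largest figure, 32%, requires 40% stopping, a fourfold hazard and no contribution from the 28-day scan. The timing key includes "If scan has not been obtained within previous 2 cycles", which may make that scan conditional, but it is unclear which cell this belongs to, and no error is asserted there.

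It is also true that the trial is described as exploratory, that PFS carries no threshold or decision, and that sampling error exceeds the bias. The last point limits the severity but does not remove the problem: a confidence interval shows sampling error and does not show this bias.

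**Conclusion.** The gap is real and minor. After the 28-day visit the plan has no rule for obtaining progression dates in patients who stop for toxicity or investigator discretion without progression. Median PFS and duration of clinical benefit are therefore at risk of upward bias.

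The size cannot be derived from the documents. On the stated assumptions, with a post-stop hazard ratio of 2-4, censoring makes the median about 2-5% too long if progression is observed for 28 days after stopping, 5-21% if only about 7 days are gained, and 6-32% if the 28-day scan adds nothing. At a hazard ratio of 1 censoring is harmless, but dating missed progressions at death gives about 5-14%, with the 28 days credited and 4 months assumed from progression to death.

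The primary response rate and both decision rules are untouched.

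**What to change.** In footnote l, for patients who stop without progression, record at the existing 3-monthly contact:

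- the date and result of each brain and extracranial scan done in routine care;
- the date of progression;
- the start of any new anticancer therapy.

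Continue until progression, death or the existing one-year limit. Use these dates for PFS and benefit duration, and state the event and censoring rules. Add a sensitivity analysis that counts a stop for toxicity or investigator discretion as an event. In the illustration its median is ln 2/(λ + σ) = 3 × (1 − f), which is 2.4 months at 20% and 1.8 at 40%, below the true median in the matching rows. It therefore gives a lower bound to set beside the main estimate.

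The cost is a few extra fields at a contact that already takes place, with no new visit or study scan. Routine scans are irregular and often prompted by symptoms, so the bias is reduced and not removed. Patients who withdraw consent to data collection are not reached. Reported medians may be slightly shorter.

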* Note that the timing of assessments may be varied by reasonable adjustments to the times indicated for scheduling or logistical issues. Patients whose on study laboratory tests were done > 7 days prior to starting treatment and whose clinical condition has changed between the time of these tests and the initiation of treatment will have a repeat chemistry panel prior to the start of treatment.

Dose Levels:

Level	Dose of TPI 287 (mg/m²)
Level - 1	140
Starting dose/Level 1	160
Level 2	180
Level 3	200
Additional dose level increases in 20 mg/m² increments	

CTCAE version 4 will be utilized in this protocol.

Study Enrollment:

The study population for this research will consist of participants from:

Only at MDACC

Estimated Accrual:

Total Accrual at MDACC: 69
 Estimated monthly accrual at MDACC: 0-1

Accrual Comments:

All patients will be accrued MD Anderson Cancer Center

Is this an NCI-Cancer Therapy Evaluation Protocol (CTEP)? No

Is this an NCI-Division of Cancer Prevention Protocol (DCP)? No

Statistical Considerations:

This is an open label, Phase 1/2, exploratory trial evaluating the efficacy and safety of TPI 287 in patients with refractory or recurrent brain metastases from breast cancer.

The primary objective of the Phase 1 portion of the study is to determine the MTD of TPI 287 and in the Phase 2 portion of the study whether TPI 287 can provide clinical benefit for patients with metastatic breast cancer to the brain following failure of prior therapy, as measured by overall response rate.

TPI 287 will be administered intravenously at an initial dose of 160 mg/m² once every three weeks. Dose escalation will continue in cohorts of 3 patients who will receive increasing doses until 1 out of 3 experience a dose limiting toxicity (DLT) at which time an additional 3 patients will be added at that dose. If ≥ 2 patients experience a DLT, the MTD will be considered the prior dose level. Dose levels will be 160 mg/m², 180 mg/m², 200 mg/m² and then increased in 20 mg/m² increments until the MTD is reached.

Once the MTD has been reached an initial cohort of 25 patients will be enrolled; if at least 5 patients are shown to have an objective response, an additional 26 patients will be enrolled.

The following data sets will be used in this study:

- All enrolled and eligible subjects (ITT) population: All eligible subjects who signed the informed consent form.

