- All treated and eligible patients (Safety and Efficacy evaluable) population: All patients who received at least one dose of study drug

Efficacy analyses will be performed on the Safety and Efficacy evaluable population in the patients on Phase 2. Safety analysis will be performed on the Safety and Efficacy evaluable population in both portions of the study.

The primary outcome measure will be response rate in the Phase 2 portion of the study. A two-stage patient accrual plan is used for this portion. Based on historical data, responses to chemotherapy in this disease ranged from approximately 30 to 55%; however in most cases these were combined with whole brain radiation therapy. Therefore, a 15% response rate to single agent

chemotherapy will be targeted as a reasonable outcome for this patient population. We target this response rate of 15% because our experience in this heavily pre-treated patient population indicates that almost none of the patients of the patients will respond under the current best-supportive care/hospice care regimen. We used trial and error to get a two-stage design with reasonable operating characteristics for $p_0 = 15\%$. One such design would have 25 patients in the first stage and 26 patients in the second stage. It would continue onto the second stage if more than 4 patients had response in the first stage. The trial would be considered a success if 11 or more out of the total 51 patients had response. This trial has a false positive (alpha) rate of 11% (under $p_0 = 15\%$) and a false negative (beta) rate of 12% (under $p_1 = 30\%$). The trial also has a probability of early termination under p_0 (i.e., if the true response probability is $p_0 = 15\%$) of 68%.

Data Safety Monitoring Board / DSMB at MDACC:

Select the name of the data safety monitoring board (DSMB) monitoring this protocol:
Not Applicable

Please explain:
This study open label and not randomized.

Protocol Monitoring:

Does this protocol have a schedule for interim and final analysis? No

Provide a rationale for no interim analysis.

This is not a randomized study.

Protocol Monitoring Plan:

The protocol will be monitored by MDACC IND office

Intellectual Property:

1. Does this study include any agents, devices, or radioactive compound (or drug) manufactured at MD Anderson Cancer Center or by a contract manufacturer? No

Investigational New Drugs (IND):

Does this protocol require an IND? Yes

Who is the IND Holder/Regulatory Sponsor?

MDACC

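### A dose cleared on 0 of 3 patients can become the Phase 2 dose; requiring at most 1 DLT in six there is a cheap, modest improvement

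*Combined protocol and SAP*

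**What the plan says.** The escalation rule is in Proposed Treatment/Study Plan and is repeated in Statistical Considerations.

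- With no DLT in three patients, the dose goes up by 20 mg/m² in a new cohort of three. The cleared level is not expanded.
- With one DLT in three, "an additional 3 patients will be enrolled in that cohort".
- With two or more DLTs at a level, "the MTD will be the previous dose level tested". No minimum number treated at that level is given.
- "Patients on the Phase 2 portion of the study will be enrolled at the MTD determined during Phase 1".
- A DLT needs both a first-cycle event and failure to recover. For a non-haematological event of grade 3 or more, it is one "that does not improve to Grade 1 or baseline within 3 weeks".

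In Phase 2, "Once the MTD has been reached an initial cohort of 25 patients will be enrolled". Five or more responses in those 25 lead to 26 more. That is the only trial-level accrual decision stated. Treatment of an individual patient ends for, among other reasons, "unacceptable toxicity, withdrawal of consent, or discontinuation based on Investigator discretion". The DSMB entry is not applicable. Under Protocol Monitoring the form reads "Does this protocol have a schedule for interim and final analysis? No". The IND office monitors the protocol, with no DLT threshold stated. Estimated Accrual gives "Total Accrual at MDACC: 69", at 0-1 patients a month.

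**The concern.** The MTD and safety are the Phase 1 primary objective, and the MTD then sets the dose for 25 to 51 patients. Three patients without a DLT say little about that dose: the one-sided 95% upper limit on the DLT rate is 63%. Because a level is expanded only after a DLT, a three-patient MTD is the usual outcome of this rule. Dose levels are open-ended above 200 mg/m², where the document describes no experience on the three-weekly schedule. A level that is too toxic could be carried forward on thin evidence when three more patients, who are to be enrolled in any case, would give a better check.

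**Working it through.** **Inputs.** From the document: cohorts of three, expansion to six only after 1 of 3, MTD one level below the first level with two or more DLTs, 69 patients in total and 51 in Phase 2. So 69 − 51 = 18 places remain for Phase 1. The document gives no DLT rates and no target rate. All true DLT rates below are assumptions.

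**Plan's own figures.** None are given for Phase 1. For Phase 2 (continue with more than 4 of 25, success with 11 or more of 51), the exact two-stage binomial gives alpha 0.107, beta 0.124 and early termination 0.682. These match the stated 11%, 12% and 68%.

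**1. Strength of 0/3.** The one-sided 95% upper limit is 1 − 0.05^(1/3) = 63%. After 0/6 it is 1 − 0.05^(1/6) = 39%. After 1/6 it is 58% (exact).

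**2. Accepting one level with true DLT rate p.**

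- Plan: (1−p)³ + 3p(1−p)² × (1−p)³
- At most 1 of 6: (1−p)⁶ + 6p(1−p)⁵

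| p | Plan | At most 1 of 6 |
|---|---|---|
| 20% | 0.512 + 0.384 × 0.512 = 0.709 | 0.262 + 0.393 = 0.655 |
| 40% | 0.216 + 0.432 × 0.216 = 0.309 | 0.047 + 0.187 = 0.233 |

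**3. Whole escalation.** This is an exact recursion over the escalation rule, starting at 160 mg/m² and leaving out Level −1. The base curve is 10%, 20%, 30%, 40% and so on.

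| | No Phase 1 limit | 18 places |
|---|---|---|
| Declared MTDs resting on three patients | 74% | 76% |
| MTD with true rate ≥ 40%, plan | 9.8% | 4.6% |
| Same, with six-patient confirmation | 7.7% | 3.2% |
| Trials with at least one level rejected on confirmation | 9.0% | 7.7% |

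With 18 places, 7.2% of trials run out of places before an MTD is declared. Over six assumed curves with 18 places, the chance of an MTD at 40% or more runs from 0.8% to 23.0% under the plan and from 0.4% to 17.3% with confirmation. The top value comes from a curve that jumps from 15% at 180 mg/m² to 40% at 200 mg/m².

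**4. Time to classify a DLT.** 21 days for onset plus up to 21 days for recovery gives up to 42 days. At one patient a month or fewer, that defers one or two patients.

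**5. A further boundary in Phase 2.** Take a boundary of one third after a 0/3 MTD, with looks at 6, 12, 18 and 24 patients and limits of 2, 4, 6 and 8 DLTs. It triggers in 18%, 31%, 47% and 78% of cases at true rates of 20%, 25%, 30% and 40%. For a 40% dose, an average of 12.03 of the first 25 Phase 2 patients are treated at that dose. If the rest are one level lower at 30%, expected DLTs are 12.03 × 0.4 + 12.97 × 0.3 = 8.7. The three replacements after a rejection (probability 0.352) add 0.352 × 3 × 0.3 = 0.3, giving about 9.0 against 10.0 with no rule. On the base curve with 18 places, about 15.0% of trials trigger: 11.9% at true rates of 30% or less and 3.1% at 40% or more.

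**The case against.** Several points on the other side are sound.

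- **Prior exposure.** The Rationale cites over 100 treated adults, no DLT at 185 mg/m² every three weeks with bevacizumab (in glioma, patient number not given), and no toxicity at 125 mg/m² weekly for three weeks of four. This lowers the risk at 160 and 180 mg/m², so the gap matters mainly from 200 mg/m² upward.
- **Slow accrual and existing monitoring.** This is one centre, open label, with weekly first-cycle blood counts, adverse-event monitoring, a safety analysis in both phases and IND-office oversight. Most 21-day windows close before the next patient enrols. A reader might infer that Phase 2 has no safety protection; the document does not support that.
- **Small effect on assumed curves.** Confirmation leaves about 70% to 80% of the risk in place (3.2/4.6 and 7.7/9.8), and nothing in the document favours one curve. It also rejects a 20% dose declared on 0/3 in 10.4% of cases, and the Rationale chose this schedule in the hope that higher doses work better.
- **Incomplete text.** The document is in abstract form and refers to a Section 5 on study drug administration that is not in it. A rule could be there.

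One defence fails. The two-DLT rule at any dose level sits in the escalation paragraph and defines the MTD. Applied to Phase 2 it would act at 2 of 25, which is not workable.

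**Conclusion.** The point holds in a limited form. As written, a level cleared on 0/3 can become the dose for 25 Phase 2 patients with no one else treated there first, and on the base curve about three quarters of declared MTDs rest on three patients. Six-patient confirmation is conventional, uses patients already planned, and gives a modest gain: acceptance of a true 40% dose falls from 31% to 23%. The trial-level figures depend on assumed DLT curves.

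A reader might go further and conclude that the plan must carry a numerical DLT boundary throughout Phase 2. The document does not support that as a requirement. It states no target DLT rate from which to derive a boundary. On the base curve a one-third boundary would trigger far more often at doses of 30% or less than at the doses it is meant to catch, and even at a true 40% it would save about one DLT per trial. Such a trigger is optional.

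The severity is minor.

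**What to change.** Declare an MTD only if at most 1 of six patients treated at that dose has a DLT.

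- If the level was cleared on 0/3, the first three Phase 2 patients complete the six. Their DLT status is known before anyone else enrols.
- If two or more of the six have DLTs, drop one level under the same rule. Those three patients stay in the safety analysis but do not count towards the 25 or 51.
- Add replacement patients to the planned 69.

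Optionally, keep a running count of first-cycle DLTs in Phase 2 with a stated review trigger. The boundary is the sponsor's choice and should prompt review only. If the dose is later lowered, state that patients treated at the abandoned dose are not pooled in the 5-of-25 and 11-of-51 response test. If the full protocol already has these rules, cite them in Statistical Considerations instead.

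**Cost.** A few sentences of protocol text and one pause of up to six weeks. Three replacement patients are needed for each rejected level. On the base curve with 18 places this happens in 7.7% of trials, and more than three are needed in under 1%. If Phase 2 runs to 51, these replacements take a further 1.9% of trials past 69 (about 1% to 3% over the six curves). Acceptance of a 20% dose falls from 71% to 66%. Replacements after a later, optional de-escalation are not in these figures: by the look at 24, 24 − 3 = 21 Phase 2 patients could have been treated at the abandoned dose.

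### Does answering 'No' to an interim analysis schedule leave the Phase 2 stop/go look undefined or alter its error rates?

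*Combined protocol and SAP*

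**What the plan says.** In the combined protocol and SAP, the Protocol Monitoring section answers a standard question with "Does this protocol have a schedule for interim and final analysis? No". The next prompt, "Provide a rationale for no interim analysis", is met by the statement that the study is not randomized.

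Statistical Considerations describes Phase 2 as a two-stage design of 25 and then 26 patients. On the first stage it says: "It would continue onto the second stage if more than 4 patients had response in the first stage". Success is 11 or more responders of 51. The stated properties are alpha 11% at a 15% response rate, beta 12% at 30%, and a 68% chance of early termination at 15%. Proposed Treatment/Study Plan gives the same rule from the other side: "if at least 5 patients are shown to have an objective response, an additional 26 patients will be enrolled".

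Three further statements bear on timing and denominator:

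- Timing note 7 of the Table of Procedures and Assessments places on-study brain MRI "Within 7 days prior to odd numbered cycles".
- Estimated Accrual gives "Estimated monthly accrual at MDACC: 0-1".
- Statistical Considerations says "Once the MTD has been reached an initial cohort of 25 patients will be enrolled", and also "Efficacy analyses will be performed on the Safety and Efficacy evaluable population in the patients on Phase 2". That population is defined as patients who received at least one dose.

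**The concern.** A rule that stops the trial when 4 or fewer of the first 25 patients respond is an interim futility analysis. Denying that a schedule exists contradicts it, and lack of randomization is no reason, since single-arm two-stage designs have such a look by construction. Someone reading only the monitoring section would not learn that a stop/go decision is due.

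Two loose ends sit beside this. The look is triggered by a patient count, and the supplied text does not say that all 25 must have been assessed for response first. The 25 are also described as enrolled, whereas efficacy is analysed in treated patients. If the count were taken too early, or if never-dosed patients used up places, the cut-off of 5 would be applied to fewer than 25 assessable patients. An active drug would then be dropped more often than the stated 12% beta allows for.

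**Working it through.** **Inputs from Statistical Considerations.** n1 = 25, n2 = 26; continue if X1 ≥ 5; success if X1 + X2 ≥ 11; p0 = 0.15, p1 = 0.30.

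**Formulas (exact binomial).**

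- Early stop: PET(p) = P(X1 ≤ 4 | 25, p).
- Success: S(p) = Σ over x = 5 to 25 of P(X1 = x | 25, p) × P(X2 ≥ 11 − x | 26, p).
- Alpha = S(0.15); beta = 1 − S(0.30).

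**Step 1: reproduce the plan's figures.**

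| Quantity | Stated | Computed |
|---|---|---|
| PET at 15% | 68% | 0.6821 |
| Alpha | 11% | 0.1068 |
| Beta | 12% | 0.1237 |

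PET at 30% is 0.0905. So of the 12.4% beta, 9.0 percentage points come from stopping at the look and 12.4 − 9.0 = 3.4 points (rounded) from missing 11 of 51 at the end.

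**Step 2: take the 'No' literally.** With no look, success is simply 11 or more of 51. Then alpha = 0.1333 and beta = 1 − 0.9327 = 0.0673. Neither agrees with the stated 11% and 12%, and a 68% early-termination probability would have no meaning. The stated figures therefore identify the two-stage reading as the intended one.

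**Step 3: how many of the 25 could lack a scan?** *Assumption, not in the documents: the count is taken on the day the 25th patient has a first dose.* Cycles last 21 days, so Cycle 3 begins 42 days after first dose and the first scan falls on days 35 to 42.

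- At 1 patient a month (gap 30.4 days), patient 24 is at day 30.4 and patient 25 at day 0, so two are unscanned. Patient 23, at day 60.8, has been scanned.
- At 0.5 a month (gap 60.8 days), only patient 25 is unscanned.

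**Step 4: error rates under that assumption.** The cut-off of 5 is applied to the scanned patients. The others count at the end if the trial goes on.

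| Scanned at the look | PET at 15% | Alpha | PET at 30% | Beta |
|---|---|---|---|---|
| 25 | 68.2% | 10.7% | 9.0% | 12.4% |
| 24 | 71.3% | 10.1% | 11.1% | 14.1% |
| 23 | 74.4% | 9.5% | 13.6% | 16.2% |

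**Step 5: denominator.** *Assumption: one never-dosed patient in each stage, not replaced, cut-offs unchanged.* With 24 and then 49 treated, alpha is 8.6% and beta 15.6%. With none never-dosed, nothing changes.

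**Step 6: cost of waiting.** For an assumed wait of 6 to 12 weeks at 1 patient a month, 6 × 7 / 30.44 = 1.4 and 12 × 7 / 30.44 = 2.8 enrolments are deferred.

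**The case for a change.** The best case for a change is that the contradiction is explicit, the reason given for it is not valid, and the remedy is a line of text. The monitoring section also lists the data safety monitoring board as not applicable, so it nowhere signals the decision. A premature count does harm in the direction that matters: the chance of wrongly stopping a drug with a 30% response rate goes from 9.0% to 13.6% with two patients unscanned.

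The inconsistency in the form answer stands. The rest is weaker, for four reasons.

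- Changing 'No' to 'Yes' would not fix a follow-up time, so the form answer is not the cause of the timing gap. Read literally, 'No' would also deny a final analysis, although the success rule at 51 patients is plainly one.
- The study plan makes the second-stage patients conditional on five responses having been shown, and sets no deadline for showing them. On that wording, accrual waits at 25 until the condition is met, and a later response still counts. A first stage of 25 naturally means all 25 assessed.
- The efficacy set is already named as treated patients, which settles the denominator for the analysis. How many patients would never be dosed is not given anywhere.
- The supplied text is an abstract page that refers to a Section 5 and to MRI obtained per protocol, neither of which is included. Silence here on the assessment window does not show that the full protocol is silent.

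**Conclusion.** The answer in Protocol Monitoring is a clerical slip. It conflicts with a rule given consistently in Proposed Treatment/Study Plan and Statistical Considerations, and that rule governs. Applied as written, with all 25 assessed before a stop is declared, it yields 10.7% alpha, 12.4% beta and 68.2% early termination, which are the stated values after rounding. Rewriting the form answer would alter no cut-off, sample size or conclusion.

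The less favourable figures are hypothetical. Beta of 14.1% to 16.2% needs a permanent stop declared with one or two known patients still unscanned, and the upper value also needs accrual at the top of the stated range. Beta of 15.6% needs an assumed never-dosed patient in each stage, with no replacement. The text directs neither. Waiting for the last scans costs little at this accrual rate, so there is no practical pressure to count early. Follow-up before the look and the treated-patient denominator are conventions an analyst would apply correctly without further instruction. No change to the plan is needed.
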